5.1. Background

Rate adaptive pacing may improve exercise capacity in subjects with chronotropic incompetence [1-5]. A number of sensors have been used to adjust pacing rate for rate adaptive pacing [6]. Medtronic rate adaptive pacing algorithms use a single axis accelerometer to adjust pacing rate during activity. Micra device is a single chamber ventricular pacemaker implanted in the right ventricle which uses a three-axis accelerometer. The recordings from all three accelerometer vectors may provide information on subject posture and allow for determination of the optimal accelerometer vector to be used for rate adaptive pacing. The accelerometer of Micra device is also capable of sensing heart motion and thus may detect atrial and ventricular contraction. Characterization of the intracardiac accelerometer signal may allow for the development of methods to synchronize ventricular pacing with atrial contractions, and consequently, the ability to provide atrioventricular synchronized pacing. This would potentially broaden the pacemaker indications for which the Micra implantable device may be used.

A previous clinical research study called the Micra Accelerometer Sensor sub-Study (MASS) collected accelerometer data and electrical heart activity of subjects implanted with a Micra device, during various postures and 24 hours of daily living. MASS used electrocardiogram (ECG) data to characterize accelerometer signal as motion associated with the atrial contraction. However, the source of the motion sensed by the accelerometer remains unclear. Understanding the source of the sensed motion may allow for the development of methods to synchronize ventricular pacing with atrial contractions. The recording of cardiac echo data, in addition to ECG data, may help to understand the elements contributing to the sensed activity and consequently may provide the ability to deliver atrioventricular synchronized pacing. This would potentially broaden the pacemaker indications for which the Micra implantable device may be used.

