MASS2 procedures will be similar to MASS. After subject enrollment, the investigational MATS software will be downloaded into the implanted Micra device and the subject will be equipped with the Holter for the time of the posture and exercise tests. As in MASS, the MATS software will allow telemetry transmission of sensor data from the implanted Micra device to the Holter. The additional procedure introduced in MASS2 compared to MASS is the echocardiography recording. The echo recording will be done after the posture and exercise test using the echo equipment available at the hospital. The collected echo recordings will be used to understand the source of the signals from the intracardiac accelerometer. After the echo recording, the Holter will be removed from the subject and the MATS software will be manually removed from the Micra device. After the software removal, the subject will be exited from the study. The Holter overnight recording, which was optional in MASS, will not be part of MASS2.

Every effort will be undertaken to minimize missing data (e.g. periodic assessment of the accelerometer, ECG and echo data).

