10.2. Site activation

Before performing study related activities, all requirements shall be fulfilled, including, but not limited to the following:

- EC approval (and voting list, as required by local law) of the current version of the Clinical Investigation Plan (CIP) and ICF.
- Regulatory authority approval or notification (as required per local law)
- Fully executed Clinical Trial Agreement (CTA)
- Curriculum Vitae (CV) of investigators and key members of the investigation site team (as required by local law).
- Documentation of delegated tasks
- Documentation of study training.

Additional requirements imposed by the EC and regulatory authority shall be followed, as appropriate.

Medtronic may distribute pre-populated study-specific Investigator Site File (ISF) and will provide site with documentation of study center/investigator readiness. Evidence of center/investigator readiness must be received prior to subject enrollment and must be filed in the ISF.

11. Study Procedures

Subject may be at the hospital specifically for the MASS2 or for other reasons independent from MASS2, such as routine clinical care. Subject will undergo following study procedures:

- **Informed consent procedure** - The subject will be screened to verify eligibility criteria and willingness to participate to the study. After both subject and investigator sign and date the ICF, the subject is considered enrolled.
- **Baseline, Medical History** – Collect Baseline and Medical History information
- **Micra Implant Procedure History** – Collect information on the previous Micra implant procedure
- **MATS software download** - After subject enrollment, the investigational MATS software will be downloaded into the implanted Micra device.
- **Holter examination** - The subject will be equipped with the investigational ER220 Holter and Holter telemetry will be turned ON. The duration of transmission of Holter telemetry data is recommended to be set at 4 hours and should not exceed 24 hours. The subject will be requested to perform a posture and exercise test. The test consists of a repetition of postures and exercises for each of the three rate response activity vectors (V1, V2 and V3), such as:
 - If the subject is not being paced, temporary overdrive pacing at approximately 10 bpm above the intrinsic heart rate for 30 seconds
 - Supine, right recumbent and left recumbent postures for 1 minute each
 - Sitting and standing for 1 minute each

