11.4. Prior and Concomitant Medications

There is no restriction about prior or concomitant medication/treatment. Subjects who had already received MATS software in MASS can receive MATS software download again in MASS2.

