12.1. Potential Risks

Medtronic follows rigorous Quality Assurance and Control procedures throughout the development and clinical study of a product. The formal Hazard/Risk analysis of MATS Research System was done for the MASS study according to ISO 14971 (Medical Device Risk Management) and was used to ensure that the level of risk is acceptable prior to starting the MASS study.

MASS2 will use the same MATS Research System used in MASS (Table 1) and for the same purpose to allow collection of data from the Micra sensors. MASS2 procedures are similar to MASS. The main change in procedures is the addition of the echo examination performed with the echo machine available at the hospital. The echo procedure poses negligible / no risk to the subjects. Therefore, the formal Hazard/Risk analysis of MATS Research System which was done for MASS will not be impacted by MASS2, due to no new or increased risk as an outcome of the study. The comprehensive Hazard Analysis is documented in the MATS Research System Risk Management Report (DSN017848 Version 2.0 Initial Release).

During the course of the MASS2 study, risks will be continuously monitored, assessed and documented by the investigators. The risks are reduced as much as possible, with residual risk being documented within the Risk Management Report and disclosed in the ICF provided to subjects. A list of potential risks, mitigations and risk controls associated with the MASS2 product and procedure is summarized in Table 3 and Table 4.

This document is electronically controlled. Printed copies are considered uncontrolled.

Confidential

Any potential risks associated with this study are further minimized by selecting qualified investigators, training study personnel on the Clinical Investigation Plan and User Manual.

Table 3 - Potential product risks and risk minimization

Potential product risk	Minimization

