
Device longevity:
 
The sensor functionality and telemetry uplink mode will cause a slight current drain on the Micra device.
	
 Risk control measures have been implemented to prevent longevity impacts greater than three months by limiting the duration of uplink of sensor data using telemetry to a maximum of 24 hours The MATS feature set has an internal timer that automatically deactivates the software 48 hours after download The MATS software download into the Micra Device will be prevented if the device is at pre-RRT (Recommended Replacement Time)

This document is electronically controlled. Printed copies are considered uncontrolled.

Confidential

Table 4- Potential procedure risks and risk minimization

Potential procedure risk	Minimization
Excessive exertion from MASS2 Posture and Exercise Test may worsen subject's health conditions.	
 Subjects will not be enrolled in the MASS2 if unwilling or not able to perform study requirements Subject is allowed to have recovery time during the test as needed.
Inappropriate pacing: The procedure includes steps to set temporary pacing rate approximately 10 bpm above the subject's intrinsic rhythm to collect accelerometer data during pacing	
 Subjects are under the supervision of an experienced Clinician during the protocol steps Detailed instructions in the MASS2 worksheets instructing overdrive pacing at a rate ~ 10bpm higher than the intrinsic heart rate Temporary pacing allows immediate cancellation / cessation of pacing if needed due to subject symptom There are no potential interactions of the MATS software with the temporary parameters of the Micra device

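### A device re-used from MASS could pass the 24 h uplink limit behind Table 3's three-month longevity bound, because no stated rule counts its earlier uplink

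*Combined protocol and SAP*

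**What the plan says.** Table 3 in Section 12.1 names device longevity as a product risk. Its one quantitative control is meant to "prevent longevity impacts greater than three months by limiting the duration of uplink of sensor data using telemetry to a maximum of 24 hours". It does not say whether 24 h applies to each download or to the device over its life. Two further controls are listed: "The MATS feature set has an internal timer that automatically deactivates the software 48 hours after download", and a block on download once the device is at the pre-replacement battery stage.

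Section 11.4 puts no restriction on prior treatment and adds: "Subjects who had already received MATS software in MASS can receive MATS software download again in MASS2". On MASS2 itself, Section 11 says that the telemetry duration "is recommended to be set at 4 hours and should not exceed 24 hours". Table 2 schedules 4 h, Section 11 has telemetry switched off after the echo, and Section 7.1 expects about 2 h from enrolment to exit.

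On MASS, Section 5.1 says data were collected "during various postures and 24 hours of daily living", and Section 7 says: "The Holter overnight recording, which was optional in MASS, will not be part of MASS2".

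Section 12.1 carries the MASS hazard analysis over. It reasons that "The main change in procedures is the addition of the echo examination performed with the echo machine available at the hospital" and concludes that the analysis "will not be impacted by MASS2, due to no new or increased risk as an outcome of the study".

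**The concern.** Battery drain adds up over the life of an implant. The longevity statement rests on a cap on hours, yet the plan lets the same device be used in a second study without asking how many hours it used in the first. The 48 h timer restarts with each download. The battery block catches only devices near replacement. The access code (Section 8.1.3) is specific to each device, but no check of earlier uplink is attached to it. Neither the eligibility criteria nor Table 2 contains such a check. The argument for carrying the hazard analysis over does not mention a second uplink on the same device.

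At stake is battery life in a permanently implanted pacemaker, in a study that Section 12.2 says may bring the subject no benefit. Only subjects returning from MASS are exposed to this. The study data and their analysis are not touched.

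**Working it through.** **Inputs from the documents**
- Uplink limit: 24 h, tied to at most 3 months (Table 3).
- MASS2 uplink: 4 h scheduled (Table 2), 24 h permitted (Section 11).
- Whole visit: about 2 h (Section 7.1). This is an upper value for uplink in a normal visit, since it also covers consent, history, download and removal.
- MASS enrolment: 40 subjects, with 20 recordings processed in sinus rhythm (Section 7.2).

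**Assumptions**
- MASS uplink per device is not given. I take 12 to 24 h for a long recording and 2 to 4 h for a device with the posture test only.
- Uplink in MASS did not itself exceed 24 h.

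**The plan's own figure.** The link between 24 h and three months cannot be reproduced, because neither current drain nor battery capacity is given.

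**Total uplink = MASS hours + MASS2 hours**

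| MASS hours | + 2 h (normal visit, upper value) | + 4 h (timer runs out) | + 24 h (permitted ceiling) |
|---|---|---|---|
| 12 | 14 | 16 | 36 |
| 20 | 22 | 24 | 44 |
| 22 | 24 | 26 | 46 |
| 23 | 25 | 27 | 47 |
| 24 | 26 | 28 | 48 |

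Against the limit, 26/24 = 1.083 (8% over), 28/24 = 1.167 (17% over) and 48/24 = 2 (double).

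**Prior uplink at which 24 h is reached**
- Normal visit: 24 − 2 = 22 h.
- Timer runs out: 24 − 4 = 20 h.
- Permitted ceiling: 24 − 24 = 0 h, so any returning device would pass the limit.

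**Posture test only in MASS.** Totals run from 2 + 2 = 4 h to 4 + 4 = 8 h, well inside the limit at the scheduled setting.

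**How long uplink lasts in a visit.** The scripted test takes 3 vectors × (0.5 + 3 + 2 + 2 to 3 min) = 22.5 to 25.5 min, before recovery time and echo. If uplink were 1 h (an assumption), the total after 24 h in MASS would be 25 h and the threshold 24 − 1 = 23 h.

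**What the excess could mean, assuming drain is linear in hours**
- If 24 h costs the full three months, the cost is 3 × 26/24 = 3.25 months at 26 h, 3 × 28/24 = 3.5 at 28 h and 3 × 48/24 = 6 at 48 h. At 30.4 days per month the excess is about 8, 15 and 91 days.
- Three months still holds if 24 h costs no more than 3 × 24/26 = 2.77 months (for 26 h) or 3 × 24/28 = 2.57 months (for 28 h).

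**Proposed timer rule: the smaller of 4 h and (24 − MASS hours).** 12 h prior gives 4 h (total 16), 20 h gives 4 h (total 24), 21 h gives 3 h (total 24), 22 h gives 2 h (total 24) and 24 h gives none. No case passes 24 h.

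**The case against.** **The deciding facts lie outside these documents.** Table 3 is a summary. The full hazard analysis is in the Risk Management Report and operating detail is in the User Manual; neither is provided, and either may hold a cumulative limit. Three months is an upper bound, not a measured cost, and Table 3 calls the drain slight. This stands. A reader might infer that the longevity bound is broken; the documents do not show that.

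**The affected group may be empty.** It needs a subject who was in MASS, returns, is not in atrial fibrillation on the day, and had a long recording. Section 5.1 speaks of 24 hours of daily living, while Section 7 calls the optional recording overnight, which may have been much shorter. This stands too. It would be wrong to read the MASS enrolment of 40 as an estimate; it is only a ceiling.

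**Actual uplink is shorter than the visit.** This is correct. One might infer that every device above 22 h of prior uplink would pass 24 h in a normal visit. The documents support only that it could.

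**The limit may be meant per download.** This does not help. The three-month statement would then cover one download, and the plan would give no bound for the two that Section 11.4 allows.

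**Echo is called the main change, not the only one.** That is fair, and the sentence is not false. But the conclusion of no increased risk is drawn without considering repeat uplink.

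**A 4 h maximum does not solve the cumulative problem and applies to subjects who are not at risk.** It is true that 24 + 4 = 28 h still passes the limit. But the maximum cuts the permitted total from 48 h to 28 h and costs a visit of about 2 h nothing. It also means that only devices with more than 20 h of prior uplink can pass 24 h.

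**No document says that uplink per device was recorded in MASS.** This stands, so the fix needs a default where no record exists.

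**Conclusion.** The gap is real, and it is small at the scheduled setting. As written, the plan does not keep total uplink on a returning device within the limit that supports its own longevity statement. For a device with the full 24 h used in MASS, the total is up to about 26 h in a normal visit and 28 h if the 4 h timer runs out. The 48 h figure is what the text permits, not what the schedule leads one to expect.

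This rests on three assumptions: some MASS devices had uplink above about 20 to 22 h, some of those subjects return, and no cumulative check exists in the documents not provided. The day counts also assume linear drain and that 24 h costs the full three months; that second assumption is the least favourable case. This is an inexpensive safety improvement for the sponsor to consider, not evidence of harm.

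**What to change.** 1. **Section 11:** replace the 24 h ceiling on telemetry with a 4 h maximum, as Table 2 already schedules. This limits drain for every subject and is twice the expected visit length.
2. **Section 11.4 and Table 3:** state that 24 h is a total per device. Before issuing the access code for a returning device, the Study Team checks its MASS uplink where recorded. If the device had the long recording and no record exists, assume 24 h. Set the timer to the smaller of 4 h and the remaining allowance. Do not download again if the remainder is too short for the planned recording; a fixed 22 h cut-off is not needed.

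Alternatively to item 2, with item 1 in place: if the sponsor's drain data show that 28 h costs no more than three months, say so in Table 3 and leave Section 11.4 unchanged.

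**Cost:** one check per returning subject, at a step where the Study Team already issues a code for each device. How easy the check is depends on what MASS recorded. A few returning subjects, with their echo recordings, may be lost; new enrolments can fill those places.

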12.2. Potential Benefits

The MASS2 may offer no benefit. It is possible that improved rate response settings may be programmed as a result of the test. Improved rate response may provide improvements for optimal pacing rate.

12.3. Risk-Benefit Rationale

The data collection and procedural steps for MASS2 are assessed to be complete and sound in investigating improvement to rate response using the sensors in the Micra pacemaker, with all risks identified having been reduced to as low as possible for subjects' and investigators' safety.

13. Adverse Event Assessments

13.1. Definitions/Classifications

For the purposes of the clinical report, Medtronic will classify each adverse event according to ISO 14155:2011.

Where the definition indicates "device", it refers to any device used in the study. This might be the device under investigation, or any market released component of the system.

Adverse Event (AE): (ISO14155:2011 3.2)

Any untoward medical occurrence, unintended disease or injury, or untoward clinical signs (including abnormal laboratory findings) in subjects, users or other persons, whether or not related to the investigational medical device

NOTE 1: This definition includes events related to the investigational medical device or the comparator.

This document is electronically controlled. Printed copies are considered uncontrolled.

Confidential

NOTE 2: This definition includes events related to the procedures involved.

NOTE 3: For users or other persons, this definition is restricted to events related to investigational medical devices.

Adverse Device Effect (ADE): *(ISO14155:2011 3.1)*

Adverse event related to the use of an investigational medical device

NOTE 1: This definition includes adverse events resulting from insufficient or inadequate instructions for use, deployment, implantation, installation, or operation, or any malfunction of the investigational medical device.

NOTE 2: This definition includes any event resulting from use error or from intentional misuse of the investigational medical device

Serious Adverse Event (SAE): *(ISO 14155:2011 3.37)*

An adverse event that

- a) led to death,
- b) led to serious deterioration in the health of the subject, that either resulted in
 - 1) a life-threatening illness or injury, or
 - 2) a permanent impairment of a body structure or a body function, or
 - 3) in- subject or prolonged hospitalization, or
 - 4) medical or surgical intervention to prevent life-threatening illness or injury or permanent impairment to a body structure or a body function,
- c) led to fetal distress, fetal death or a congenital abnormality or birth defect.

NOTE: Planned hospitalization for a pre-existing condition, or a procedure required by the CIP, without serious deterioration in health, is not considered a serious adverse event.

Serious Adverse Device Effect (SADE): *(ISO 14155:2011 3.36)*

Adverse device effect that has resulted in any of the consequences characteristic of a Serious Adverse Event.

Unanticipated Serious Adverse Device Effect (USADE): *(ISO 14155:2011 3.42)*

Serious adverse device effect which by its nature, incidence, severity or outcome has not been identified in the current version of the risk analysis report

NOTE: Anticipated serious adverse device effect (ASADE) is an effect which by its nature, incidence, severity or outcome has been identified in the risk analysis report.

Device deficiency: *(ISO 14155:2011 3.15)*

Inadequacy of a medical device with respect to its identity, quality, durability, reliability, safety or performance

NOTE: Device deficiencies include malfunctions, use errors, and inadequate labelling.

13.2. Reporting of Adverse Events

All subject adverse events and device deficiencies will be collected starting from time of subject enrollment, until the exit of the subject. The AE e-CRF will be used for collecting event information, including date of event, seriousness, relatedness, resolution. Based on the risk assessment of the MATS

This document is electronically controlled. Printed copies are considered uncontrolled.

Confidential

Research System and results from the MASS, there are no anticipated or foreseeable adverse events expected to be related to MASS2 products or procedures.

Adverse Event and device deficiency information will be reported to Medtronic, immediately but no longer than 3 calendar days after the investigator first learns of the event or of new information in relation with an already reported event. Initial reporting may be done by phone, fax, e-mail (Medtronic Study Contact List will be provided on a separate cover) or by completion of the AE e-CRF. In case the investigator requires information from the sponsor in an emergency situation, the investigator can contact study contact personnel (Medtronic Study Contact List will be provided on a separate cover).

In case an adverse event is not completed at the time of the subject exit, the subject shall be asked to be followed by the physician for collecting safety data outside the clinical study.

Medtronic will immediately review any new/modified Adverse Event or Device Deficiency. This review will include the determination whether the Adverse Event meets regulatory reporting requirements (Table 5). Source documents to support adjudication may be requested by Medtronic. The sponsor will ensure timely Adverse Event reporting to meet global regulatory requirements.

Medtronic will immediately report any Adverse Events or Device Deficiencies associated with the procedure or the device to the appropriate Medtronic Complaint Handling Unit. The appropriate Complaint Handling Unit will ensure prompt review, and appropriate reporting.

Table 5 - Adverse Event reporting requirements

Serious Adverse Device Effects (SADE), including Unanticipated Serious Adverse Device Effect (USADE):	
Investigator submit to:	
Medtronic	Immediately after the investigator first learns of the event or of new information in relation with an already reported event.
Regulatory Authority	As per local reporting requirement.
EC/IRB	Submit to EC/IRB per local reporting requirement.
Sponsor submit to:	
Regulatory Authorities	Reporting timeframe as per local requirement.
EC/IRB	Submit to EC/IRB per local reporting requirement.
Serious Adverse Events (SAE)	
Investigator submit to:	
Medtronic	Immediately after the investigator first learns of the event or of new information in relation with an already reported event.
Regulatory Authority	As per local reporting requirement.
EC/IRB	Submit to EC/IRB per local reporting requirement.
Sponsor submit to:	
Regulatory Authorities	Reporting timeframe as per local requirement.
EC/IRB	Submit to EC/IRB per local reporting requirement.
Adverse Device Effects (ADE)	
Investigator submit to:	

This document is electronically controlled. Printed copies are considered uncontrolled.

Confidential

Medtronic	Immediately after the investigator first learns of the event.
Regulatory Authority	As per local reporting requirement.
EC/IRB	Submit to EC/IRB per local reporting requirement.
Sponsor submit to:	
Regulatory Authorities	Reporting timeframe as per local requirement
EC/IRB	Submit to EC/IRB per local reporting requirement.
All other AEs	
Investigator submit to:	
Medtronic	Submit in a timely manner after the investigator first learns of the event.
Regulatory Authority	As per local reporting requirement.
EC/IRB	Submit to EC/IRB per local reporting requirement.

